measures of these cognitive functions have been studied using EEG recording (Gazzaley, 2011; Pratt et al., 2011). Our recent work demonstrated that Veterans with mild TBI and PTS showed a working memory deficit when cognitive control functions were more heavily taxed (Honzel et al., 2014). In that study, we examined working memory for letters maintained across a delay that was either unfilled, or filled with a challenging distractor task. The patients were slightly less accurate than controls on the unfilled (single task) version, but impaired to a disproportionate extent on the dual task version. Furthermore, a neural index of memory retrieval processes was unaltered in the patients for the single task version but decreased for the dual task (*difference wave at Cz, dual task:  $t(30)=2.704, p=.011$ , Cohen's  $d=.956$* ). This event-related potential (ERP) "old/new" effect differentiates correctly remembered old items from correctly rejected new items, beginning at 300 ms post-stimulus and continuing for several hundred ms (Rugg & Curran, 2007). This task will allow us to assess brain activity and task performance before and after training, to test the prediction of an increase in the ERP old/new effect after training.

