**Sample Size Calculation:** We powered the study based on prior group differences (mtBI/PTS vs. Controls). We used data from the Sternberg task (Honzel et al., 2014) to obtain an estimate of the standard deviation of the ERP old/new effect, and expected effect size based on a mixed effects ANOVA (subject as random effect) with group as the sole explanatory variable. To estimate sample size, we used the two sample *t* test as an approximation to the mixed effects ANOVA and used the method of variance inflation to account for the additional subject factors (Hsieh et al., 2003). We powered based on the primary experimental question at 80% and will control false discovery rate at 5% (Benjamini & Hochberg 1995) at the time of analysis for tests of other design and subject factors. The Sternberg data showed a mean difference between the patient and control groups of -1.097 with residual error of 0.956 from the mixed effects ANOVA. Using these values in a two-sample *t* test for mean difference, to obtain 80% power we need a sample size of 13 per group. *This pilot study will allow us to collect data to inform power calculations for future studies.*’

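### The value 0.956 is Cohen's d in Preliminary Studies but the SD in the Sample Size Calculation; if it is d, 80% power needs 19 per group, not 13 (two-sided 0.05 assumed)

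*Combined protocol and SAP*

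**What the plan says.** Under Research Design and Methods, the Sample Size Calculation opens with "We powered the study based on prior group differences (mtBI/PTS vs. Controls". It draws on Sternberg-task data from the cited prior study "to obtain an estimate of the standard deviation of the ERP old/new effect", with the expected effect taken from a "mixed effects ANOVA (subject as random effect) with group as the sole explanatory variable". The inputs are a "mean difference between the patient and control groups of -1.097 with residual error of 0.956 from the mixed effects ANOVA". A two-sample t test serves as an approximation, and the authors say they "used the method of variance inflation to account for the additional subject factors". The result is stated as "to obtain 80% power we need a sample size of 13 per group". Neither alpha nor sidedness is given for this calculation; the 5% in the paragraph is a false discovery rate for tests of other factors. The Participants paragraph plans 20 trained and 20 untrained Veterans.

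Preliminary Studies, item (4), describes the patient-control difference in the old/new effect from the same prior study ("difference wave at Cz, dual task"). It reports "t(30)=2.704, p=.011", followed by a Cohen's d of .956.

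**The concern.** One three-digit value from one prior study, for one endpoint and one pair of groups, is a standardised effect in one section and a standard deviation in another. These are different quantities: d is the mean difference divided by the SD. They coincide only when the mean difference equals the SD squared, which is not so for 1.097 and 0.956 (0.956² = 0.914).

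The 13 per group depends directly on 0.956 being the SD, and this paragraph is the plan's only sample-size justification. If the value is really d, the assumed effect is overstated (1.147 instead of 0.956). The apparent margin between what is required and the planned 20 then shrinks from seven per group to one. No dropout allowance is stated, so that margin matters. The paragraph also says that this pilot will inform later power calculations, and a mislabelled SD could be carried into them.

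**Working it through.** **Inputs.** Mean difference -1.097 and 0.956, labelled residual error (Sample Size Calculation); t(30) = 2.704, p = .011, d = .956 (Preliminary Studies, item 4); 80% power; 20 per group planned (Participants). Assumed: alpha 0.05 two-sided, equal groups. Power is from the noncentral t distribution.

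**1. Reproduce the plan's figure.** With 0.956 as the SD, the standardised effect is 1.097 / 0.956 = 1.147. The two-sample t test then needs n = 12.96, so 13 per group (power 80.1%). The plan's arithmetic is sound under that reading. One-sided 0.05 would give 10.14, so 11.

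**2. Check the label in Preliminary Studies.** On 30 df there are 32 participants. With 16 per group, d = t × sqrt(1/n1 + 1/n2) = 2.704 × sqrt(2/16) = 0.956, and the two-sided p is .0112. A 15/17 split would give 0.958. The value is therefore arithmetically a d there.

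**3. Test the two places against each other as one contrast, 16 per group.**
- With difference 1.097 and SD 0.956: t = 1.097 / (0.956 × sqrt(2/16)) = 3.25, p = .003. The reported values are 2.704 and .011.
- With difference 1.097 and t = 2.704: SD = 1.097 / (2.704 × sqrt(2/16)) = 1.147, not 0.956.

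So both statements cannot hold for the same contrast. (The figure 1.147 appears twice because 1.097 / 0.956 is the effect size if 0.956 is the SD, and the SD if 0.956 is d.)

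**4. Consequence if 0.956 is d.** Required n = 18.19, so 19 per group. Power by number per group:

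| n per group | SD = 0.956 (d = 1.147) | d = 0.956 |
|---|---|---|
| 13 | 80.1% | 64.8% |
| 18 | 91.7% | 79.6% |
| 19 | 93.1% | 81.8% |
| 20 | 94.2% | 83.8% |

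At one-sided 0.05 with d = 0.956, the requirement is 14.26, so 15 per group; power is 76.5% at 13 and 90.7% at 20.

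**5. If 0.956 is a genuine model residual.** If several observations per subject entered a model with subject as a random effect, the residual leaves out between-subject variance. A t test on subject-level values needs the total SD of those values. The documents do not give the between-subject component, so the required n could be above or below 13.

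**6. Variance inflation.** At the effect of 1.147, a final 13 implies a factor of 13/12.96 = 1.003 from a two-sided t test, 13/11.92 = 1.09 from the normal approximation, or 13/10.14 = 1.28 from a one-sided t test. The text does not say which applies.

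**The case against.** The strongest reply is that the two sections may describe different quantities. Preliminary Studies reports a t test on a difference wave at one electrode in the dual task. The Sample Size Calculation reports a mixed-model residual without naming electrode or condition, and the ERP Data Analysis section defines the measure at midline electrodes in the plural. The mismatch in step 3 is a contradiction only if the contrast is the same. This stands: a reader might infer that a copying error is established, and the documents do not establish it.

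A reader might also infer that nothing in the text supports 0.956 as an SD. That goes too far. The paragraph says its aim was to estimate the SD of the effect, and if one value per subject was modelled, residual SD and pooled SD would be the same. Treating the subject as a random effect points towards repeated observations but does not settle it. If the residual error were a variance, the SD would be sqrt(0.956) = 0.978 and the requirement 13.50, so 14 per group, almost unchanged.

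Nor can one infer that the variance inflation was not applied. An uninflated two-sided t test already gives 13, but so would other combinations of method and factor (step 6).

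Finally, the practical effect is limited: the plan enrols 20 per group, not 13, and calls itself a pilot. That is fair, but the paragraph still makes a specific 80% power claim, and it should rest on an identified input.

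**Conclusion.** The point holds as an unresolved conflict over one input, with a conditional size. Entering d as the SD is the likely explanation, since the d label is confirmed by its own t statistic and the same digits recur; it is not proven. If 0.956 is d, the requirement is 19 per group instead of 13, and 13 gives 64.8% power. The planned 20 gives 83.8% before any dropout or variance inflation, and 18 completers per group fall just short at 79.6%. These figures assume two-sided 0.05, equal groups and a t test on one value per subject.

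Two stronger readings should be resisted. A reader might infer that the study is underpowered; for this prior effect with 0.956 as d, 20 per group still exceeds 19. A reader might equally infer that enrolment is confirmed as adequate; that holds only under the same reading and for that same effect. If 0.956 is a within-subject residual, the direction of any change is unknown. In either case the calculation concerns patients versus controls, so neither 13 nor 19 is power for trained versus untrained or for pre versus post.

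**What to change.** Check 0.956 against the prior study's output, and state what it is, with electrode and task condition.

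- If it is d: restate the requirement as 19 per group for 80% power and about 84% at the planned 20 (two-sided 0.05), before dropout or variance inflation.
- If it is a residual from a repeated-measures model with subject as a random effect: recompute with the total between-subject SD of the subject-level old/new effect, and compare the result with 20 per group.
- If it is the SD of the subject-level effect for a different contrast: say so and name the contrast; 13 per group then stands at two-sided 0.05.

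In every case, state alpha, sidedness and the inflation factor with the n it produces. Label the figure as power for the prior patient-versus-control effect, not for the study's own comparisons. The cost is one look at existing output and a corrected paragraph. Procedures and analyses are unaffected; whether 20 per group still meets the stated power depends on what the check shows.

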## Experimental Design

### EEG of Working Memory with and without a secondary attention task

Rationale: Previous studies in this population have shown a decline in WM performance that is exacerbated by increased task demands (Honzel et al., 2014). An established EEG marker of WM retrieval, the ERP old/new effect, indexed this impairment. Another EEG marker, frontal midline theta, is a sensitive correlate of working memory load (Gevins et al., 1997) that exhibits increases in power during cognitive demands for WM (Onton et al., 2005). This experiment will test the hypotheses that (a) patients will show changes in these markers with training; and (b) the EEG changes will explain variability in behavioral changes as measured by the operation span score and the attention/executive function composite score. We will examine EEG and behavioral performance on the Sternberg WM task alone and when the flanker interference task is performed during the maintenance period. Preliminary results from the training intervention suggest that improvements in working memory, attention, and executive functions can occur. Temporally sensitive EEG measures may elucidate the neural correlates of these changes, and help to explain individual differences in treatment response.

Experimental Design: The study will use the methods of Honzel et al. (2014), briefly described below.

Single-Task Condition (Sternberg Memory Task): Participants will be asked to remember either one or four consonants. After an 8500 ms delay, another consonant will be presented (probe). Participants respond with a button press to indicate whether the probe was part of the previous memory set (old) or whether the

probe was not part of the memory set (new).

**Single-Task Condition (Arrow Flanker Task):** Participants will be instructed to respond with a button press to indicate whether the central arrowhead points to the left or the right. Flanking arrows, positioned either above, below, or both above and below the central arrow, can point in either the same (congruent) direction (40% of trials) or different (incongruent) direction (60% of trials). Each flanker stimulus is presented for 200 ms, with the next trial beginning 300 to 500 ms after a response was made.

**Dual-Task Condition (Sternberg Memory Task + Arrow Flanker):** Participants will be required to perform the arrow flanker task during the delay interval of the Sternberg memory task. Nine flanker trials begin 300 to 500 ms following the presentation of each memory set. The stimulus parameters are the same as for the single-task flanker. The Sternberg probe is then presented 500 ms following the final flanker trial, and participants respond to indicate whether this item was in the previous memory set.

**Statistical Analysis:** The ERP old/new effect will be analyzed using a mixed effects ANOVA controlling for task (single, dual), set size (one, four), and time point (pre, post). The primary neuropsychological outcome measures will be included in the models as appropriate to assess changes from pre- to post-training. To examine the effects of repeated testing, differences in ERP mean amplitudes between patient groups (trained, untrained), task, and set size will be also be tested using a separate mixed effects ANOVA to control for random effects due to subject. Pre/post differences in Sternberg WM accuracy will be tested using a hierarchical generalized linear model. Time-frequency responses will be analyzed with the same mixed and linear models, with separate calculations for each frequency band, and a repeated measures model including all frequency bands.

**Predicted Results:** We predict that Veterans who show cognitive gains with training (based on neuropsychological measures) will show an increase in the ERP old/new effect in the dual task condition. Additionally, as prior work has shown that WM impairment in ADHD is characterized by decreased levels of alpha power during encoding, and compensatory increases in theta during maintenance (Lenartowicz, et al. 2014), we predict that cognitive gains will be reflected by changes in theta and alpha power over frontal scalp. Importantly, we can determine with precise temporal resolution whether the neural manifestations of training improvements occur during WM encoding, maintenance, and/or retrieval. Additional analyses will determine whether these EEG markers can predict which patients will improve with training.

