quantified by computing mean amplitudes in defined latency windows relative to a 100 ms pre-stimulus baseline. The primary measure will be the ERP “old/new effect” elicited during memory retrieval, time-locked to probe onset. This will be quantified by subtracting mean amplitude for Old – New probes (300-500 ms post-stimulus) at midline electrodes (Honzel et al., 2014).

**EEG Time-Frequency and Network Analysis:** Off-line analysis for resting state and dual task data will be performed in the EEGLAB Matlab toolbox (Delorme & Makeig, 2004). Data will be filtered with bandpass limits of 0.1 to 55 Hz using a standard FIR filter and re-referenced to the average of mastoid electrodes. Periodic artifacts, such as eyeblinks, will be removed using the Infomax Independent Component Analysis (ICA) algorithm. Remaining data will be further band filtered into four frequency bands (theta: 4-8 Hz, alpha: 8-13 Hz, beta: 15-30 Hz, & gamma: 30-55 Hz), and power envelope and phase angle will be extracted with a Hilbert transform.

Resting state connectivity will be calculated over two second epochs using a graph theoretical approach comparing each pair of electrodes in each frequency band, based on correlation of band power changes, and degree of phase coherence. *As we are working with resting state data, we have no a priori hypothesis about directionality of information flow. Therefore, correlations of these measures will suffice (Bastos & Schoffelen, 2016), thereby decreasing computation demands.* Spurious connectivity will be corrected by eliminating neighboring electrode connections and ignoring electrode pairs with 0 degrees of phase lag. Remaining electrode pairs will be adjusted to a common threshold to control number of network connections across patients. From these binarized connectivity matrices, modularity and characteristic path length (CPL) will be calculated using the Matlab toolbox, EEGNET (Hassan, et al. 2015). Time-frequency responses to dual task conditions will be calculated using Hilbert transformed data, epoched and averaged over the same time window and baseline as ERP analysis.

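### The plan says it can place training effects in memory encoding, maintenance or retrieval, but no maintenance window is defined, and any such window in the dual task also holds flanker activity that no stated contrast removes

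*Combined protocol and SAP*

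**What the plan says.** The design has three conditions (Experimental Design, EEG of Working Memory): Sternberg alone, with an 8500 ms delay and no flanker task described in it; arrow flanker alone; and the two combined. In the combined condition, "Participants will be required to perform the arrow flanker task during the delay interval of the Sternberg memory task". On timing, "Nine flanker trials begin 300 to 500 ms following the presentation of each memory set", and "The Sternberg probe is then presented 500 ms following the final flanker trial". The flanker displays have the same parameters as in the flanker-only condition, where the next trial starts 300 to 500 ms after each response.

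The ERP model lists task (single, dual), set size (one, four) and time point (pre, post). For band power, "Time-frequency responses will be analyzed with the same mixed and linear models". No interaction is named. The separate model comparing trained and untrained groups lists group, task and set size.

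Under EEG Time-Frequency and Network Analysis, "Time-frequency responses to dual task conditions will be calculated using Hilbert transformed data", with the same window and baseline as the ERP analysis. ERP Data Analysis sets that window at -100 to +900 ms, and the primary ERP measure is locked to probe onset. No other time-locking event is given for power.

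The Rationale supports frontal midline theta on the ground that it "is a sensitive correlate of working memory load". The Predicted Results say the study can determine "whether the neural manifestations of training improvements occur during WM encoding, maintenance, and/or retrieval".

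**The concern.** To attribute a change in power to one memory stage, the analysis needs a window covering that stage and a contrast in which other activity drops out. For maintenance, the plan specifies neither.

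During the dual-task delay the participant watches and answers nine flanker displays while holding the letters in mind, so power recorded there reflects both activities. The training targets attention under distraction, which the flanker task exercises. Flanker-related power could therefore change with training even if maintenance does not.

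The untrained group does not resolve this. It controls for repeated testing, whereas a training-induced change in flanker handling would appear only in the trained group. Correlation with behavior does not resolve it either. The attention/executive composite includes the Color-Word Inhibition and Inhibition/Switching subtests, which also draw on interference control, so better interference control alone could produce the predicted correlation.

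At stake is the mechanistic conclusion: a change in handling distraction could be reported as a change in memory maintenance.

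**Working it through.** **The plan's own figure.** The only relevant number is 13 per group, which concerns the ERP old/new effect. With d = 1.097/0.956 = 1.147 and an assumed two-sided 0.05, a two-sample t test has 76.6% power at 12 per group and 80.1% at 13. The figure reproduces, and this point does not affect it.

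**Step 1: what the stated window can cover.** The epoch lasts 100 + 900 = 1,000 ms.

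- *Locked to the probe.* The probe comes 500 ms after the final flanker trial, so the epoch starts 500 - 100 = 400 ms after it. It covers retrieval. Flanker activity can enter only through the 100 ms baseline (400 to 500 ms after the last flanker trial) and any carry-over. Maintenance is not measured.
- *Locked to the memory set.* Flankers start 300 to 500 ms after the set. Counted from set onset, the last 900 - 500 = 400 ms to 900 - 300 = 600 ms of the epoch falls in the flanker stream. Counted from set offset, the overlap depends on display duration, which is not given. An encoding epoch can therefore contain flankers too.
- *Placed inside the dual-task delay.* The longest gap without a flanker trial is 500 ms. A 1,000 ms epoch cannot fit, whatever the response time.

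**Step 2: which contrasts remove the flanker part.** Assume power is additive: M1 or M4 for memory at set size one or four, plus F for the flanker task. The cells are Sternberg alone (M1, M4), dual (M1 + F, M4 + F) and flanker alone (F). Because the contrasts are linear, the same weights apply to pre-post changes.

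| Contrast | M1 | M4 | F | In the plan? |
|---|---|---|---|---|
| Dual-task mean | 0.5 | 0.5 | 1 | Pre-post change available from the listed factors |
| Dual minus Sternberg alone | 0 | 0 | 1 | Task factor listed |
| Dual, set size four minus one | -1 | 1 | 0 | Set size listed; its interaction with time not named |
| Dual minus flanker alone | 0.5 | 0.5 | 0 | Not planned |

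The change in mean dual-task power carries the whole flanker change. Under additivity the task contrast is the flanker component itself. The last two contrasts remove F, and neither is named as a change over time. A main effect of set size does not test whether the load effect changed with training. Crossed with set size, the single level of task can only be Sternberg alone, so the flanker-only blocks enter no stated model.

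**Step 3: illustration of scale, on assumed values.** Take flanker response times of 0.4 to 0.7 s (not in the documents) and midpoint intervals of 0.4 s.

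- Delay = 0.4 + 9 × RT + 8 × 0.4 + 0.5 s, which is 7.7 s at RT 0.4 and 10.4 s at RT 0.7.
- Share of the delay between flanker onset and response = 9 × RT / delay: 3.6/7.7 = 47% and 6.3/10.4 = 61%.
- Suppose only flanker power changes. A paired t test in the 20 trained Veterans (two-sided 0.05, unadjusted) is then significant 25%, 56% or 84% of the time for shifts of 0.3, 0.5 or 0.7 SD of the within-person change.
- Under the same supposition, a load contrast is significant about 5% of the time. That is simply the test's alpha.

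**The case against.** The strongest reply is that the written window is the ERP window. Read as probe-locked, it holds no flanker display, so the planned retrieval power is largely protected. That stands, and it limits the point to maintenance and, depending on time-locking, encoding. It does not rescue the stage claim, because a probe-locked window says nothing about maintenance.

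Second, the design already contains set size, a flanker-free Sternberg condition and a flanker-only condition with matching displays, and interactions are not ruled out. This also stands: what is missing is a named analysis, not data.

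Third, the plan predicts that cognitive gains in general will show in theta and alpha, and better handling of distraction is an intended training effect. A dual-task power change is therefore a legitimate result. Only the statement about stages requires the two sources to be separated.

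Fourth, the primary EEG measure is the Old-minus-New ERP difference. The preceding flanker stream is common to both probe types and largely cancels, and the study calls itself a pilot. This is fair and bears on the weight of the point.

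**Conclusion.** The point holds for the stage inference from dual-task power. As written, a maintenance effect is either not measured (probe-locked window) or mixed with flanker activity that no named contrast removes (window in the delay). The conclusion about the window rests only on the documents' timings. The conclusion about contrasts assumes that memory and flanker power add.

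A reader might infer more than this, and the documents do not support it:

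- *That the planned power measure is dominated by flanker activity over 47 to 61% of the delay.* No power measure spanning the delay is written, and the response times behind those percentages are assumed.
- *That false memory findings will occur 25 to 84% of the time.* Those are generic paired-test power values at assumed shifts. The documents give no flanker-related shift, and the calculation ignores the planned false discovery rate control.
- *That there is no flanker-only reference.* It is in the design but not in the stated analysis.
- *That overall power is the wrong marker and must be replaced.* Keeping it or replacing it is a trade-off. The documents do not say that the stage claim rests on overall dual-task power alone.

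The size of the bias is therefore unknown. The change is worth making because it is cheap and the mechanistic conclusion depends on it.

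**What to change.** 1. State the time-locking event, window and baseline for encoding, maintenance and retrieval, separately for the single and dual tasks.
2. Base statements about maintenance on (a) the flanker-free delay of the single-task Sternberg condition, stating explicitly that its band power will be computed, and (b) a pre-specified time-by-set-size contrast within the dual task, compared between trained and untrained groups.
3. Run the same pre-post power model on the single-task flanker blocks. Describe a dual-task change that also appears there as not specific to memory.
4. Keep overall band power as planned.
5. Report flanker response time by set size, before and after training.

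The cost is analysis-plan wording and some extra processing of conditions already in the design; no new testing is needed. The load contrast has drawbacks. It is noisier than overall power, it captures only activity that depends on load, and it relies on flanker activity being similar at both set sizes. Item 5 lets a reader judge that last assumption. The comparison in item 3 is a reference for interpretation, not a formal test that separates the two sources. If no maintenance window is added, the claim to locate effects by stage should be limited to the stages that are measured.

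### No listed ERP model contains both group and time, so the plan names no between-arm comparison of change with which to test the effect of training

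*Combined protocol and SAP*

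**What the plan says.** All references are to the combined protocol and SAP. Under Experimental Design, in the working-memory EEG experiment, the Rationale states two hypotheses: (a) "patients will show changes in these markers with training", and (b) "the EEG changes will explain variability in behavioral changes". The Statistical Analysis paragraph then lists these analyses:

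- **Old/new effect:** "analyzed using a mixed effects ANOVA controlling for task (single, dual), set size (one, four), and time point (pre, post"). Group is not listed, and the arms that enter the model are not stated.
- **Separate ANOVA:** "To examine the effects of repeated testing, differences in ERP mean amplitudes between patient groups (trained, untrained), task, and set size". Time is not listed, and the sessions that enter are not stated.
- **Neuropsychological measures:** "The primary neuropsychological outcome measures will be included in the models as appropriate to assess changes from pre- to post-training".
- **Accuracy:** "Pre/post differences in Sternberg WM accuracy will be tested using a hierarchical generalized linear model".
- **Time-frequency:** "Time-frequency responses will be analyzed with the same mixed and linear models".

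Elsewhere, ERP Data Analysis makes the old/new effect the primary ERP measure. Study design and participant flow says that the untrained arm is there to show how EEG and other measures change on retesting without training, and that allocation is pseudo-random with matching on demographics. The section on neuropsychological assessments bases training effects on pre-post change scores and names no comparison between arms.

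**The concern.** Hypothesis (a) is a claim about training. In a design with two arms and two sessions, the contrast that separates training from a second exposure to the task is the difference between arms in change, or an equivalent baseline-adjusted difference at the second session. No listed model states either.

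The pre/post model attributes to training any shift that comes from being tested again. The group model, with time absent from its factors, compares levels and not changes. The untrained arm was enrolled to supply this separation, so the gap concerns the primary ERP measure and the main purpose of the control arm.

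Alternate forms or repeat-testing norms are planned for the neuropsychological tests. No such step is stated for the ERP, accuracy or time-frequency measures.

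**Working it through.** **The plan's own figure.** Sample Size Calculation gives 13 per group for 80% power, from a difference of 1.097 and a residual error of 0.956. A two-sample t test (two-sided 5%, assumed because the plan states no alpha for this calculation) has 80.1% power at 13 per group, so the figure reproduces. It concerns a cross-sectional difference between patients and controls, with group as the only factor. It therefore does not say which contrast tests training.

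**Factor lists side by side.**

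| Analysis | Group | Time | Task | Set size |
|---|---|---|---|---|
| Old/new ANOVA | not listed | yes | yes | yes |
| Separate ANOVA | yes | not listed | yes | yes |
| Sternberg accuracy | not listed | yes | not listed | not listed |
| Time-frequency | as the models above | as above | as above | as above |
| Neuropsychological change scores | not listed | through change | n/a | n/a |

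No row states both group and time, and no section names a group x time term.

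**Illustration 1: retest shift, no training effect.** Inputs: 20 per arm (Participants); two-sided 5%; one score per session with SD 1; shift s and pre-post correlation r, both assumed because the documents give neither. The SD of change is √(2(1−r)), so the standardised shift is s/√(2(1−r)). Rejection rates are from the noncentral t distribution. For s = 0.3:

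| r | 0.3/√(2(1−r)) | Pre/post test, trained arm (n = 20) | Pre/post test, both arms pooled (n = 40) | Between-arm test of change |
|---|---|---|---|---|
| 0.3 | 0.254 | 19% | 35% | 5% |
| 0.5 | 0.300 | 25% | 46% | 5% |
| 0.7 | 0.387 | 38% | 67% | 5% |

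With s = 0.2 the trained-arm rates are 11% to 20%, and with s = 0.1 they are 6% to 9%. The test is two-sided, so a fall of the same size is flagged as a decline equally often. Added to a real training increase, a fall masks it: the trained arm's change is training effect plus shift.

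**Illustration 2: what the group model would estimate.** Let D be a training effect present only at the second session. D = 0.956 SD is the patient-control Cohen's d for the dual task in Preliminary Studies (4). Using it assumes that training closes the whole gap, which is optimistic. Standardised effects are: sessions averaged, (D/2)/√((1+r)/2); post only, D; group x time, D/√(2(1−r)); baseline-adjusted, approximately D/√(1−r²) on 37 df.

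| r | Sessions averaged (estimates D/2 = 0.478) | Post only | Group x time | Baseline-adjusted |
|---|---|---|---|---|
| 0.3 | 45% | 84% | 70% | 87% |
| 0.5 | 40% | 84% | 84% | 92% |
| 0.7 | 36% | 84% | 97% | 98% |

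The readings that the sentence leaves open thus differ in what they estimate and in power. Group x time beats post only when 2(1−r) < 1, that is when r > 0.5.

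**The case against.** The best defence is the purpose clause of the second ANOVA. Repeated testing cannot be studied with one session, and the model compares trained with untrained patients, so pre-post differences compared between arms are a plausible intent. The stated role of the untrained arm agrees. The paragraph is also terse: the accuracy sentence omits even task and set size, so its silence on group is weak evidence of exclusion. The term mean amplitudes is the plan's general way of quantifying ERPs and does not by itself indicate averaging over sessions.

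Most of this stands, and it rules out three stronger readings.

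- A reader might infer that the untrained arm goes unused, or that no controlled comparison was intended. The documents do not support that, because a group comparison is listed.
- A reader might infer that the sessions will be averaged and the effect halved. The text permits this but does not state it, and it fits the purpose clause least well.
- A reader might infer that training effects will be inflated, or that later studies planned from these data will be too small. The documents give no retest shift in either direction. They say only that the data will inform later power calculations, not that the trained arm's change alone would be used.

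The defence does not supply the missing specification. Grammatically, the differences in the second ANOVA are between groups, and time is not a factor. A post-only reading would rely on baseline balance under pseudo-random allocation. Adding the neuropsychological measures to the models serves hypothesis (b) and the prediction that "We predict that Veterans who show cognitive gains with training (based on neuropsychological measures) will show an increase in the ERP old/new effect"; it does not compare arms for hypothesis (a).

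**Conclusion.** The point holds as a gap in specification that should be fixed before analysis. As listed, the pre/post model confounds training with retesting, the group model does not estimate change, and no between-arm test of change is named for the ERP, accuracy, time-frequency or neuropsychological outcomes. That conclusion rests on the factor lists alone.

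The size of the consequence depends on assumptions. The 19% to 38% range needs a 0.3 SD retest shift and r from 0.3 to 0.7; at 0.1 SD the excess over 5% is slight. The power figures also assume the 0.956 SD effect and reduce each session to a single score. They show that the choice of reading matters and do not forecast this trial's results.

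**What to change.** State which arms and which sessions enter each model. Then:

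1. Fit one mixed model of the old/new effect with group, time, task, set size and group x time, using both arms and both sessions.
2. Name in advance one between-arm contrast of change in the dual-task condition as the test of hypothesis (a): either group x time, or the baseline-adjusted difference at the second session.
3. Report the untrained arm's pre-to-post change as the repeated-testing estimate.
4. Add group x time to the accuracy and time-frequency models, and compare change in the attention/executive composite and operation span between arms.
5. Keep hypothesis (b) and the prediction about Veterans who show cognitive gains as separate analyses relating ERP change to behavioural change.

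Both arms are already scheduled for repeated testing, so no extra data are needed. The cost is revised wording and a few more model terms across several analyses. Group x time also has less power than a post-only test if r is below 0.5 (70% against 84% at r = 0.3 in the second illustration). The baseline-adjusted contrast avoids that loss over the range shown.
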